14.3 Quality assurance audits and regulatory agency inspections

The sponsor or the designee shall perform audit at the study site as necessary. In such a case, the auditor designated by the sponsor shall contact the study site in advance to determine the date of audit. The auditor may ask to visit the facilities where laboratory specimens are collected and any other facilities used during the clinical study. In addition, this study may be inspected by regulatory agencies, including those of foreign governments (e.g., the Food and Drug Administration [FDA], the United Kingdom Medicines and Healthcare products Regulatory Agency [MHRA]). If the study site is contacted for an inspection by a regulatory body, the sponsor should be notified promptly. The

principal investigator and the chief executive of the study site shall ensure that the auditor has access to all the study-related source documents.

15.0 ETHICAL CONDUCT OF CLINICAL STUDY

This clinical study shall be conducted with the highest respect for the individual participants (i.e., study subjects) according to the study protocol, the ethical principles that have their origin in the Declaration of Helsinki, and “Ethical Guidelines for Medical and Health Research Involving Human Subjects.” Each principal investigator will conduct the study according to regulatory requirements and in accordance with “Responsibilities of the Principal Investigator” in Appendix B.

15.1 Approval of the Ethical Review Board, etc.

The Ethical Review Board, etc., shall be constituted in accordance with the regulations.

The sponsor or the designee should obtain the document listing the name and title of each committee member. When a committee member directly participates in this clinical study, the document describing that he/she is not participating in deliberation or voting for the study will be obtained.

The sponsor or the designee shall supply relevant documents for submission to study site committee such as the Ethical Review Board for the protocol’s review and approval. In addition to the study protocol, a copy of the informed consent form and information sheet, written materials related to study subject recruitment, advertisement, and other documents required by regulations, when necessary, shall be submitted to the central committee or a study site committee such as the Ethical Review Board to obtain approval. The sponsor or the designee must obtain written approval of the protocol and the informed consent form and information sheet from the study site committee such as the Ethical Review Board before commencement of the study. The study site committee such as the Ethical Review Board’s approval must refer to the study by exact protocol title, number and version date; identify versions of other documents (e.g., informed consent form and information sheet) reviewed; and state the approval date. The sponsor shall notify the study site, the principal investigator, and investigator after confirming the validity of the regulatory documents of the study site. Protocol procedures such as obtainment of consent shall not be started until the study site, the principal investigator, and investigator receive notification.

The study site shall observe all requirements that the Ethical Review Board, etc. prescribe. The requirements may include notifications to committees such as the Ethical Review Board, for example, revision of the protocol, revision of the informed consent form and information sheet, revision of materials related to study subject recruitment, reports on safety in accordance with the regulatory requirements, reports on status of implementation of the study at intervals determined by a study site committee such as the Ethical Review Board, and submission of the study completion report. The sponsor or the designee shall obtain written approval from the Ethical Review Board, etc. related to the above mentioned items and all related materials.

CONFIDENTIAL

15.2 Conflict of interest

This clinical study shall be conducted with the support of the sponsor.

Prior to the conduction of this clinical study, the principal investigators involved in this clinical study shall ensure appropriate management of any conflicts of interest (COI) in the conduct of the study in accordance with the rules of the study site.⁹⁾⁻¹³⁾

The study site shall observe all requirements that the Ethical Review Board, etc. prescribe. This will include self-declaration of COI, clinical study protocol, informed consent form and information sheet.

15.3 Informed consent form and information sheet, and the agreement of the study subjects

The informed consent form shall contain specific requirements of the Declaration of Helsinki, Ethical Guidelines for Medical and Health Research Involving Human Subjects and all applicable laws and regulations. The informed consent form and information sheet shall specify the use of personal information and medical information of study subjects in this clinical study (both in and outside Japan: supply to a third party), and disclosure. The informed consent form will explain in detail the nature of the clinical study, its objectives, and potential risks and benefits. The informed consent form will detail the requirements of the participant and the fact that study subject is free to withdraw at any time without giving a reason and without any negative effect on further medical care.

The principal investigator is responsible for the preparation, contents, and approval of the informed consent form and information sheet by the committee such as the Ethical Review Board. The informed consent form and information sheet must be approved by the committee such as the Ethical Review Board prior to use.

The informed consent form shall be written in language that can be easily understood by the potential study subjects. The principal investigator or investigator shall be responsible for providing detailed explanation of the informed consent form to the potential study subjects. Information should be given in both oral and written form whenever possible and in manner deemed appropriate by the committee such as the Ethical Review Board.

Once signed, the original informed consent form shall be retained by the principal investigator or investigator. The principal investigator or investigator shall record the date that the potential study subject signed the informed consent form in the subject's medical record. A copy of the signed informed consent form shall be given to the study subject.

The principal investigator or investigator shall follow the same procedure as for obtaining the initial consent when newly obtaining re-consent from the concerned study subject when the informed

CONFIDENTIAL

consent form and information sheet is revised. The date of obtaining new consent shall be recorded in the study subject's medical record, and a copy of the revised consent form shall be provided to the study subject.

15.4 Personal information of the study subjects

The sponsor or the designee shall affirm the principle of the protection of study subjects' private/personal information. Throughout this study, study subject ID codes shall be used to link the subject's source data to the sponsor's study database and study-related documents. Limited information on study subjects such as gender, age, and date of birth may be used within the scope of all applicable laws and regulations for identification of study subjects and confirmation of accuracy of study subject ID code.

For verification of the conduct of the study in compliance with this protocol and the Ethical Guidelines for Medical and Health Research Involving Human Subjects, the sponsor shall require the principal investigator to provide the study sponsor's designee, representatives of regulatory authorities, designated auditors, and committees such as the Ethical Review Board direct access to study subjects' original medical records (source data or documents), including laboratory test results, admission and discharge records during a subject's study participation, and autopsy reports. The principal investigator or investigator shall obtain specific authorization of the study subject as part of the informed consent process for access to study subject's original medical records by study sponsor's designee and representatives of regulatory authorities (see Section 15.3).

When providing a copy of source documents to the sponsor, the principal investigator or investigator shall delete information that may lead to identification of an individual (name and address of study subject, other personal information not recorded on the CRF of the study subject).

15.5 Consultation windows for the study subjects or persons related to the study concerned

The principal investigator shall establish a contact service to respond to inquiries concerning this clinical study from study subjects or concerned people. Details of the contacts for inquiries will be described in the informed consent form and information sheet.

15.6 Financial burden or reward to the study subjects

Of the expenses for this clinical study, the sponsor shall offer compensation for medical treatment not covered by health insurance as study expenses. The study subjects shall pay expenses for medical treatment covered by ordinary health insurance.

In addition, the principal investigator shall pay expenses such as transportation expenses for participation in this clinical study to the study subjects at each visit from the research funds. Details

CONFIDENTIAL

of the financial burden on the study subjects and rewards shall be described in the informed consent form and information sheet.

15.7 Benefits and inconveniences to the study subjects

15.7.1 Benefits to study subjects

Study subjects can deeply learn their own conditions of type 2 diabetes including such as the change in the QOL associated with the change in treatment approaches and the level of treatment satisfaction, through the study participation

15.7.2 Inconveniences to study subjects

Burdens of study subjects may be increased due to requirements of providing answers to the Basic Information on Study Subject, DTR-QOL Questionnaire and DTSQ, through the study participation.

15.8 Attribution of study results and access rights

15.8.1 Attribution of study results

The study results and data obtained from this study shall belong to the sponsor. In addition, secondary use (meta-analysis, etc.) of the data obtained in this clinical study may be possible if used in such a way that the data shall not be linked to personal identification information.

15.8.2 Data access rights

Access rights for all data and information generated from this study will be given to personnel approved by the sponsor.

15.9 Reporting of results, publication, disclosure, and clinical study registration policy

15.9.1 Reporting of results, publication and disclosure

The principal investigator shall report a written summary of results of the study to the chief executive of the study site and provide the sponsor with all the results and data obtained from the study. Only the sponsor may disclose the study information to other principal investigators, investigators or regulatory authorities during the study period, except when required by laws and regulations. The sponsor shall be responsible for publication of the study protocol and study-related results (including the public web site) except for other cases permitted in the study contract.

During the study period and after the end of study, the sponsor or the designee should promptly summarize the results and present it to medical journals and academic conferences, etc. The sponsor

may publish any data or information obtained from the study (including data and information provided by the principal investigator) without obtaining agreement of the principal investigator.

The principal investigator or the investigator should obtain the prior written approval from the sponsor when publishing the information obtained in this study at an academic conference, etc.

15.9.2 Clinical study registration

To ensure that information on clinical study is made accessible to the public in a timely manner and to comply with applicable laws, regulations, and guidelines, Takeda Pharmaceutical Company Limited shall register all clinical study being conducted in patients around the world at public trial registration sites, including at least the website(s) of ClinicalTrials.gov (and) Japan Pharmaceutical Information Center Clinical Trials Information (JAPIC), before initiation of the clinical study. On such websites, the study location (city, country), study subject recruitment status, and contact information for Takeda Pharmaceutical Company Limited are open to the public.

15.9.3 Clinical trial results disclosure

Takeda Pharmaceutical Company Limited shall post the study results, irrespective of the nature of the results, at the public trial registration site(s) of Clinical Trials.gov (and) JAPIC in accordance with applicable laws and regulations.

15.10 Insurance and compensation for injury

In case of injuries, each study subject in the clinical study must be insured in accordance with the regulations applicable to the study site where the subject is participating. The sponsor or the designee shall buy an insurance policy to compensate for health injury in study subjects.

Healthy injury in a study subject will be compensated as specified in the study contract. Compensation-related questions by the principal investigator or investigators should be made to the sponsor or the designee.

CONFIDENTIAL

2 EFFICACY EVALUATIONS	11
2.1 Primary Endpoint and the Analytical Methods	11
2.2 Secondary Endpoints and the Analytical Methods	11
2.3 Other Analysis	12
2.4 CONSIDERATIONS on STATISTICAL ANALYSIS	15
2.4.1 Adjustments for Covariates	15
2.4.2 Handling of Dropouts or Missing Data	15
2.4.3 Interim Analysis and Early Discontinuation	15
2.4.4 Multicenter Studies	15
2.4.5 Multiple Comparisons/Multiplicity	15
2.4.6 Use of an Efficacy Subset of Subjects	15
2.4.7 Active-Control Studies Intended to Show Equivalence	15
2.4.8 Subgroup Analysis	15
3 SAFETY EVALUATION	16
3.1 Treatment -Emergent Adverse Event	16
3.1.1 Brief Summary of Adverse Events	16
3.1.2 Display of TEAE	17
3.2 Frequency of Hypoglycemia	18

3.3 Hospitalization related to type 2 diabetes mellitus	18
4 LISTINGS.....	18
Significance level, Confidence coefficient	21
REVISION HISTORY.....	22

DEFINITIONS of TERMS

- Treatment -emergent adverse event (TEAE) : The AE which occurs after taking the first dose of trial medication.
- Summary Statistics: Number of subjects, mean, SDs, maximum values, minimum values, and quartiles
- BMI: Body Mass Index
- MedDRA: Medical Dictionary for Regulatory Activities
- QOL: Quality Of Life
- WHO: World Health Organization
- DTSQ: Diabetes Treatment Satisfaction Questionnaire
- DTR -QOL: Diabetes Therapy -Related QOL
- Subject with hypoglycemia: The subject with AE related to hypoglycemia
- Non Serious TEAE: Non -Serious TEAE is defined as Non -Serious TEAEs of at least 5% in any treatment group by SOC and PT. (if no event exceeds the 5% frequency, cutoff is lowered to 2%).

ANALYSIS SET

- Full Analysis Set
The subjects who were randomized and received at least one dose of the Trelagliptin or Daily DPP-4 inhibitor
- Safety Analysis Set
The subjects who received at least one dose of the Trelagliptin or Daily DPP-4 inhibitor

TIME WINDOW

For each assessment, observation and evaluation item, evaluable data is selected according to the following table. When there are multiple data exist within a time window, the one with the closest date to the reference date is adopted, and if the differences from the reference date are the same for multiple data, the later one is adopted.

1) DTR -QOL Questionnaire, The Basic Information on Study Subject, Laboratory Test (HbA1c)

Analysis Visit	Reference Date	Time Allowance (Number of Study Days)
Week -4	-30	-30～-15
Week 0	-1	-14～-1
Week 4	28	21～35
Week 12	84	70～97

Analysis Visit	Reference Date	Time Allowance (Number of Study Days)
End of Study	The latest date in treatment period	21～97

2) DTSQ, Laboratory Test (except HbA1c)

Analysis Visit	Reference Day	Time Allowance (Number of Study Days)
Week -4	-30	-30～-2
Week 0	-1	-1
Week 4	28	21～35
Week 12	84	70～97
End of Study	The latest date in treatment period	21～97

OTHER DATA HANDLING

Items	Method	Conditions
DTR -QOL Questionnaire Factor1: Burden on Social Activities and Daily Activities	The sum total of questions number 1 -13 was converted into a 0 -100 score [the best (91) = 100 and worst (13) = 0].	For a factor with <50% missing data, the mean value (round off 2 digits) calculated from available answers is applied to cover the missing data.
DTR -QOL Questionnaire Factor 2: Anxiety and Dissatisfaction with Treatment	The sum total of questions number 14 and 19 -25 is converted into a 0 -100 score [the best (56) = 100 and worst (8) = 0].	For a factor with <50% missing data, the mean value (round off 2 digits) calculated from available answers is applied to cover the missing data.
DTR -QOL Questionnaire Factor 3: Hypoglycemia	The sum total of questions number 15 -18, and is converted into a 0 -100 score [the best (28) = 100 and worst (4) = 0].	For a factor with <50% missing data, the mean value (round off 2 digits) calculated from available answers is applied to cover the missing data.
DTR -QOL Questionnaire Factor 4: Treatment Satisfaction	Each score of question number 26 -29 is reversed (i.e., 1 converted to 7, 7 converted to 1, and so on; the converted scores, where 7 is the best	For a factor with <50% missing data, the mean value calculated from available answers is applied to cover the missing data.

Items	Method	Conditions
	and 1 is the worst, had the opposite sequence of the original scores). The converted scores are then added up, and the total is converted into a 0 -100 score [the best (28) = 100 and worst (4) = 0].	
DTR -QOL Questionnaire Total Score of all Questions	1) Each score of question number 26 -29 was reversed.((i.e., 1 converted to 7, 7 converted to 1, and so on;). Factor1 – Factor 4 are calculated as described above.(Not converted) 2) Factor 1 - Factor 4, which calculated by the method described above, are subsequently added up, and converted into a 0 -100 score [the best (203) = 100 and worst (29) = 0].	The total score of whole questions is not calculated if a total score of any of the four factors was unavailable.
DTSQ Total Score	Item 1, 4, 5, 6, 7, 8 scores are added up,	All data must not be missing.
Planned Number of Dosage of Trelagliptin (tablets)	(The last administration date - the first administration date) / 7) +1. * Cut off to the whole number	All data must not be missing.
Planned Number of Dosage of Daily DPP -4 Inhibitor (tablets)	(The last administration date - the first administration date) \times number of daily dose \times number of tablets at the first administration date	All data must not be missing.
Study Medication Compliance (%)	Actual number of dosage / Planned number of dosage \times 100 (tablets)	All data must not be missing.
Days after Administration (Days)	Examination/observation/evaluation date - the first administration date +1	All data must not be missing.

Items	Method	Conditions
Duration of Diabetes (year)	$\{ (\text{The first administration date (year)} \times 12 + \text{The first administration date (month)}) - (\text{Onset Date of Diabetes (year)} \times 12 + \text{Onset Date of Diabetes (month)}) \} / 12$ (rounded off two decimal places)	All data must not be missing. If only the month of the onset of diabetes is unknown, the month of the onset of diabetes is regarded as "January".
8-OHdG/Creatinine (ng/mg CRE)	8-OHdG (ng/mL) / Urine creatinine (mg/dL) $\times 100$	All data must not be missing.

Display digit

Item	Defitintion
Mean, Confidence interval, Quartiles	Round statistics down to the 1 digits lower than significant digits of the data.
Standard Deviation	Round to the 2 digits lower than significant digits of the data.
Minimum and Maximum Values	Display the data at the significant digits.
Proportion, Percentage	Round to the one decimal place.
P-value	Round down to four decimal places. If p-value is less than 0.0001, display "p<0.0001"

AE related to Hypoglycaemia

AE related to Hypoglycaemia is defined as below.

PT Code	PT Name (Japanese)	PT Name (English)
10020993	低血糖	Hypoglycaemia
10040576	低血糖ショック	Shock hypoglycaemic
10065981	低血糖性意識消失	Hypoglycaemic unconsciousness
10048803	低血糖性痙攣	Hypoglycaemic seizure
10021002	低血糖性脳症	Hypoglycaemic encephalopathy
10021000	低血糖昏睡	Hypoglycaemic coma
10020997	無自覚性低血糖	Hypoglycaemia unawareness
10054998	神経低糖症	Neuroglycopenia

1 SUBJECTS, DEMOGRAPHIC and OTHER BASELINE CHARACTERISTICS

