7.4 Study subject management

The principal investigator and investigator shall instruct the research subject the items below.

- (1) Give instructions to take allocated oral hypoglycemic drug as directed.
- (2) If hypoglycemia symptom (hunger abnormal, feeling of weakness, trembling of hands and fingers, cold sweat, palpitations, etc.) is observed, take glucose or sucrose (sugar), and if it does not improve give instructions to visit promptly.
- (3) On visit days for planned laboratory tests, give instructions not to take oral hypoglycemic drug scheduled to be taken on that day. Further, at each visit, have the research subject report if drug has been taken or not the day before, and on the day of visit.
- (4) On visit days for planned laboratory tests, give instructions for fasting \geq 10 hours before visit (excluding start of observation period).
- (5) For research subjects of childbearing potential, give instructions to use adequate contraception. If pregnancy is discovered, have the research subject report promptly, and discontinue the research immediately.
- (6) The principal investigator and investigator shall instruct the research subject to adhere to instructed prohibited concomitant drugs. When drugs are taken other than the drugs prescribed by the principal investigator and investigator, have the research subject report its content.
- (7) Regarding subjective symptoms/objective findings, have the research subject report at visit the necessary items from its contents, onset date, degree, outcome and date of outcome.

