9.1.10 DTSQ

Subjects will answer the DTSQ (all 8 questions)^{6), 7)} regarding the diabetes therapy being conducted at each assessment time point during the treatment period. The investigator will instruct the subjects to answer all questions truthfully and record the answer of each question of the DTSQ (8 questions in total) on the CRF.

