9.2.1 Screening period (Week -4)

After obtaining informed consent, the physical examination and tests will be performed for the determining eligibility for study enrollment. The eligibility of a patient will be determined based on the inclusion/exclusion criteria presented in the section 7.0. Refer to the section 9.1.16 for the preparation of records on a study subject withdrawn from the study before randomization.

Tests, observations and evaluations performed at the start of the screening period (Visit 1: Day -29 to -1) are shown below.

- Informed consent
- Inclusion/ exclusion criteria
- Demographic data, medical history
- Physical examination*
- Height, body weight and BMI
- Concomitant drugs*
- Comorbidity*
- Laboratory tests (HbA1c only) *
- DTR-QOL Questionnaire*
- The Basic Information on Study Subject (Your Basic Profile)*

*: To be performed during from Day -29 until Day -14.

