9.2.2 Treatment period (Week 0)

An eligible study subject in consequence of the tests, observations and evaluations before the start of the treatment period will be randomized in accordance with the section 8.4.

Tests, observations and evaluations performed at the start of the screening period (Visit 2: Week 0) are shown below.

- Inclusion/ exclusion criteria
- Physical examination
- Concomitant drugs
- DTR-QOL Questionnaire
- DTSQ
- The Basic Information on Study Subject (Your Basic Profile)
- Comorbidity
- Adverse event[#]
- Laboratory tests (blood chemistry and urinalysis)
- Hospitalization for type 2 diabetes[#]
- Prescription of the study drug/ or comparative drug

#: To be performed after the first administration (Day 1).

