2.2 Secondary Endpoints and the Analytical Methods

Analysis Set: Full Analysis Set

Items: 1) DTR -QOL Total Score
2) DTR -QOL Total Score of Factor1 to Factor 4
"Factor 1: Burden on Social Activities and Daily Activities" (13 questions)
"Factor 2: Anxiety and Dissatisfaction with Treatment" (8 questions)
"Factor 3: Hypoglycemia" (4 questions)
"Factor 4: Satisfaction with Treatment" (4 questions)
3) DTSQ Total Score
4) DTR -QOL Total Score of Each Items
5) DTSQ Total Score of Each Items

Analysis Visit: Week 0, Week 4, Week 12, End of Study

Method:

- (1) The following analysis will be performed for the Items 1 to 3 described above.
 Summary statistics of observed value and 95% confidence interval for the mean will be calculated by treatment groups and Analysis Visit. In addition, Mean (+/-SD) plots will be made by treatment group and Analysis Visit. Adjusted mean differences and the 95% confidence interval (two-sided) will also be provided. The same analyses described above will be performed on change from baseline at each analysis visit.
- (2) The following analysis will be performed for the Items 2 to 3 described above.
 Analysis of covariance (ANCOVA) will be conducted to compare between the treatment groups using "the change from baseline in the total score by the end of treatment [the End of Study(Week 12) - baseline (Week 0)]" as a dependent variable; the total score of "the DTR-QOL Total score (<80 or ≥ 80)" at the baseline (Week 0) and "HbA1c (<8.0% or $\geq 8.0\%$)" at the baseline (Week 0) as covariates; and "a treatment group" as an independent variable.
- (3) The following analysis will be performed for the Items 1, 3 described above.
 The summary statistics and two-sided 95% CI for means of change from baseline by treatment group will be calculated, with stratification by the following factors at the start of the treatment period (Week 0):
 - Use of medication for treatment of comorbidities;
 - Number of daily doses of medication for treatment of comorbidities (<2 times or ≥ 2 times);
 - total number of daily tablets of medication for treatment of comorbidities (<2 tablets or ≥ 2 tablets);
 - Number of doses of the study drug or comparative drug (once weekly, once daily or twice daily).
- (4) The following analysis will be performed for the Items 4 -5 described above.
 Summary statistics for measurements and the change from baseline (Week 0) will be calculated by treatment group per question at each analysis visit.

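### The SAP accepts one Week 0 day for DTSQ and eight laboratory items but 14 for DTR-QOL and HbA1c from the same visit, has no window for a first-dose-date baseline, and labels the primary time point with two visits

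*SAP*

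**What the plan says.** The Time Window section of the SAP decides which values enter the analysis: "evaluable data is selected according to the following table". Where several values fall in one window, the one nearest the reference day is used.

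- **Table 1** (DTR-QOL, basic information, HbA1c): Week -4 is Day -30 to -15 and Week 0 is Day -14 to -1, with reference Day -1.
- **Table 2**, whose heading begins "2) DTSQ, Laboratory Test (except HbA1c": Week -4 is Day -30 to -2 and Week 0 is Day -1 alone.
- **Both tables**: the next window opens at Day 21. Week 12 is Day 70 to 97. End of Study is the latest value in Day 21 to 97.

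The protocol's schedule is as follows.

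- Section 9.1.10 has subjects answer the DTSQ "regarding the diabetes therapy being conducted at each assessment time point during the treatment period", so there is none in screening.
- Section 9.2.1 limits screening laboratory work; its entry begins "Laboratory tests (HbA1c only". The footnote to the starred screening items, which include DTR-QOL and HbA1c, reads "To be performed during from Day -29 until Day -14".
- Section 9.2.2 collects DTR-QOL, DTSQ, blood chemistry and urinalysis together at Visit 2 (Week 0). The same list includes "Prescription of the study drug/ or comparative drug", and its footnote calls the first administration Day 1.
- Section 7.4 (3) says that on laboratory visit days sites must "give instructions not to take oral hypoglycemic drug scheduled to be taken on that day".

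SAP 2.2 (2) compares DTSQ change between groups by ANCOVA, with the DTR-QOL and HbA1c categories "at the baseline (Week 0) as covariates". SAP 2.4.2 leaves out values that are missing or not adopted under the data-handling rules. SAP 2.1 places the primary endpoint at End of Study (Week 12).

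**The concern.** One visit is judged by two baseline rules. If Visit 2 falls a few days before first dose, its DTR-QOL and HbA1c become Week 0 values, while the DTSQ completed at that visit becomes a Week -4 value. Week -4 is not among the analysis visits in SAP 2.2 or, for laboratory tests, in SAP 2.3, so the relabelled value is used nowhere. The subject would have both Week 0 covariates for the DTSQ ANCOVA but no DTSQ change score, and SAP 2.4.2 then excludes the subject. No scheduled assessment belongs in the table 2 Week -4 row, so all the row can do is relabel Visit 2 data.

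Both Week 0 windows also stop at Day -1, and the SAP has no fallback such as the last value before dosing. A pre-dose Visit 2 assessment on the first-dose date would have no Week 0 label for any item, including the DTR-QOL total score. The day count needed to apply the tables, Study Days, is not defined.

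The primary time-point label is a separate matter. End of Study can take a value from as early as Day 21, but Week 12 cannot. A discontinuer's early score is used under one reading and dropped under the other.

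**Working it through.** **The plan's own sample-size figure.** Protocol 13.3 asks for 110 per group. With a difference of 19.0 - 14.4 = 4.6, SD 12.1, two-sided 5% and 80% power, the normal approximation gives 2 x (1.960 + 0.842)^2 x 12.1^2 / 4.6^2 = 108.6, so 109. The two-sample t-test gives 109.6, so 110. The figure reproduces, but nothing below depends on it.

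**Window lengths.** Table 1 Week 0: -1 - (-14) + 1 = 14 days. Table 2 Week 0: 1 day.

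**Items under table 2.** SAP 2.3 lists 7 serum and 2 urine items, 9 in all. Less HbA1c, 8 fall under table 2, plus DTSQ.

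**Placing Visit 2.** Let g be the first-dose date minus the Visit 2 date. Study Days is undefined, so three day counts were tried. The third is the only day formula in the SAP (Days after Administration, under Other Data Handling); the SAP does not tie it to the window tables.

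| Day count | g = 0 | g = 1 | g = 2 | Table 1 Week 0 | Table 2 Week 0 | Visit split |
|---|---|---|---|---|---|---|
| No Day 0 | Day 1, no window | Day -1, Week 0 in both | Day -2, Week 0 / Week -4 | g = 1 to 14 | g = 1 | g = 2 to 14 |
| Plain difference | Day 0, no window | Day -1, Week 0 in both | Day -2, Week 0 / Week -4 | g = 1 to 14 | g = 1 | g = 2 to 14 |
| Date - first dose + 1 | Day 1, no window | Day 0, no window | Day -1, Week 0 in both | g = 2 to 15 | g = 2 | g = 3 to 15 |

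Under each count, 14 gaps keep the DTR-QOL and HbA1c baselines, 1 keeps DTSQ and the other laboratory items, and 14 - 1 = 13 split the visit. This counts possible gaps and says nothing about how often each occurs. At g = 0 there is no baseline under any count. Under the SAP's own formula there is none at g = 1 either.

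**A reading with no loss.** Suppose the protocol counts a Day 0 and the SAP does not. With first dose on Day 1, protocol Day -29, -14, -1 and 0 are 30, 15, 2 and 1 days before dose (1 minus the day number). In the SAP these are Day -30, -15, -2 and -1. The first three are exactly the SAP boundaries, and the fourth is the table 2 Week 0 day. Visit 2 is then the day before first dose, and every item is in window.

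**Primary time point.** End of Study spans 97 - 21 + 1 = 77 days and Week 12 spans 97 - 70 + 1 = 28. So 77 - 28 = 49 End of Study days lie outside the Week 12 window.

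**The case against.** The strongest defence is that the tables were built from the protocol schedule. Three boundaries match after a one-day shift, which is unlikely to be chance. On that mapping table 2 is simply Visit 1 followed by a Visit 2 on the day before dosing, and a baseline is lost only if Visit 2 is off schedule. This stands as a likely account of intent. However, the SAP does not state it, and its only day formula contradicts it. Appendix A and Figure 6.a, which could fix the timing of Visit 2, are not in the text available here.

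Other stronger readings are tempting and should be resisted.

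- **That the protocol contradicts itself on the first dose.** It does not. Prescribing at Visit 2 and starting on a later day satisfies both 9.2.2 and 7.4 (3). What is missing is an explicit statement of when the first dose falls.
- **That a screening score could become the baseline**, because protocol Day -14 lies in the table 1 Week 0 window. This requires both documents to number days alike, against the three boundary matches. It also requires that no Visit 2 value be in window, since the nearest-date rule would otherwise prefer Visit 2.
- **That the primary analysis loses power.** Any such figure needs a share of lost baselines, and the documents give no basis for one. Nor is it safe to say there is no reserve because 120 x 0.92 = 110.4 against 110 needed. Protocol 13.3 describes the 8% as an annual rate. At a constant rate over 12 weeks (an assumption), 1 - 0.92^(12/52) = 1.9% would discontinue, leaving 120 x 0.981 = 117.7 per group.
- **That the protocol supports both primary time points equally.** The endpoint in 5.2.1, the analysis text in the summary (2.0) and the endpoint line of 13.1.3 all say Week 12. Only the model sentence in 13.1.3 omits it. SAP 2.2 (1) already reports the DTR-QOL total at both visits, so neither result would be hidden.

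**Conclusion.** The point holds as a defect in the written rule, with an unknown number of subjects affected.

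- **DTSQ and eight laboratory items.** The mismatch of 1 day against 14 for one visit is certain from the tables. It causes loss whenever Visit 2 is not on the single accepted day, and it does not need same-day starts. It reaches one secondary endpoint with a planned ANCOVA, and laboratory summaries among the other endpoints.
- **First-dose date.** The gap exists under all three day counts tried. It reaches the primary endpoint only if some subject starts on the day of Visit 2.
- **Number affected.** It may be zero. It is zero if Visit 2 is always the day before first dose and the SAP has no Day 0. No loss of power is claimed.
- **Primary label.** What is open is which of two defined visits carries the primary test. No loss is shown, but the choice should not be left until the data are seen.

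The change is worth making because following the SAP as written can discard valid baselines, and because two programmers could build different Week 0 data from the same records.

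**What to change.** 1. For every Visit 2 item, define Week 0 as the last non-missing value after the screening visit, on or before the first-dose date and before dosing. Treat Visit 2 assessments on the first-dose date as pre-dose unless the records show otherwise. This works whenever the first dose falls.
2. Delete the Week -4 row from table 2.
3. State one study-day convention for the windows, and say whether the Days after Administration formula applies to them.
4. State in the protocol when the first dose falls relative to Visit 2, so that 7.4 (3) and 9.2.2 can be read together without inference.
5. Before the data are analysed, name either the Week 12 or the End of Study window for the primary test, and keep the other as a sensitivity analysis. Week 12 agrees with the protocol's endpoint wording; End of Study would need that wording aligned. Apply the choice also to the ANCOVAs in SAP 2.2 (2), which carry the same joint label.

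The cost is SAP text, programming edits and one protocol clarification, with no new visits. There is a small downside. The listings in SAP 4 give dose times, but only a sample date for laboratory tests and an analysis visit for the questionnaires, so some same-day values could not be verified by time as pre-dose.
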